## **F. Benefits to Subjects**

*Potential benefits of the proposed research to the subjects and others.* We do not expect participation in this study to benefit the individual participant directly. However, if the study is successful, the knowledge gained could lead to improvements in treatment efficacy, which would have a major beneficial impact on others. This information is conveyed to participants in the informed consent.

*Importance of the knowledge to be gained.* This application aims to test the hypothesis that facilitated dopamine neurotransmission boosts efficacy of fear extinction learning in PTSD. Knowledge gained from this study would critically inform current leading models of fear extinction learning as well as models of exposure therapy for PTSD. Consequently, it is expected that knowledge gained from this study would then lead to improved therapy modalities, which would have a significant impact on societal public health.

## **G. Statistical Plan**

*Power Analyses and Targeted Sample Size.* A prior study using a fear extinction methodology among healthy humans found significant effects of L-DOPA using an N of 20 in each drug group (Haaker, Gaburro, Sah, Gartmann, Lonsdorf, Meier, Singewald, Pape, Morellini, & Kalisch 2013a); the prior dopamine gene score x L-DOPA study found a significant interaction using an N of 25 for the two drug groups. Prior studies examining the effect of L-DOPA on resting-state FC have used sample sizes of < 20 per cell (Cole, Beckmann, Oei, Both, van Gerven, & Rombouts 2013a; Cole, Oei, Soeter, Both, van Gerven, Rombouts, & Beckmann 2013b; Kelly, de, Di, Copland, Reiss, Klein, Castellanos, Milham, & McMahon 2009). Using GPower software to estimate power, a sample size of 35 per drug group (total N = 105) would provide power > .9 to detect large effects and power ~.8 to detect medium-large effects.

### Data analysis.

*Primary Analytic Framework for Fear Extinction Effects.* The overall data analysis framework for Aim 1 fear extinction analyses consists of a 3 (group: placebo vs 100 mg L-DOPA vs 200 mg L-DOPA) x 2 (cue: CS+ vs CS-) x 2 (context: A [learning context] vs B [extinction context]) x 6 (dopamine gene score: 0 [low endogenous dopamine] – 5 [high endogenous dopamine]) mixed design focused on Day 2 fear responding. Preliminary analyses would test for any baseline

differences in fear responding or extinction learning on Day 1 and include these variables as covariates if needed. Analyses would also control for ancestry as well as other demographic or clinical variables should they differ between groups.

*Neural circuit ROI definition and extraction.* The neural circuit indices would be 6 *a priori* regions of interest (ROI) with anatomical coordinates defined from the recent literature (Delgado et al. 2008; Haaker, Gaburro, Sah, Gartmann, Lonsdorf, Meier, Singewald, Pape, Morellini, & Kalisch 2013a; Milad, Wright, Orr, Pitman, Quirk, & Rauch 2007; Phelps, Delgado, Nearing, & LeDoux 2004; Schiller et al. 2008) and include bilateral amygdala, bilateral hippocampus, ventromedial PFC, dorsal anterior cingulate cortex. Following standard preprocessing, first-level analyses conducted for each individual separately would consist of whole-brain GLMs, in which the task design (CS+ vs CS- during Context A vs B) is modeled as boxcar events convolved with a canonical HRF. The task design is regressed onto each voxel's timecourse within a GLM framework and using restricted maximum likelihood to account for serial correlation, resulting in a whole-brain spatial map indicating the degree to which each voxel responds to CS+ vs CS- during Context A vs B. The mean contrast values for CS+ vs CS- as a function of context is then extracted from the voxels within 6 mm spherical ROIs for the six ROIs. These analyses would provide six (for each ROI) indices of activation, calculated separately for each participant, that would be used in multivariate analysis of variance (MANOVA) analyses to define the impact of L-DOPA and dopamine gene score on consolidation of fear extinction learning.

**Planned Fear Extinction Analyses:** We would conduct three sets of MANOVA analyses, one with the set of Day 2 neural circuit indices (amygdala, dorsal anterior cingulate cortex, caudate) as dependent variables, one with the set of Day 2 physiological indices (SCR, HR, HRV) as dependent variables, and one with the set of Day 2 verbal/self-report indices (anxiety, UCS expectation) as dependent variables. In these analyses, the mixed effects of L-DOPA group, dopamine gene score, cue, context, and the interactions are entered as factors explaining variance in the multivariate combination of the set of dependent variables. Interactions with context would demonstrate the effect of the manipulations on robustness to context renewal effects. Additionally, any factors that differ between groups, such as Day 1 fear responding, age, or comorbid diagnoses, would also be entered as covariates should the balanced "urn" randomization fail. Given the three sets of tests, FDR correction (Benjamini and Hochberg 1995) would be used to control for alpha inflation. If the multivariate analyses reveal significant between-group differences in our measures of neural, psychophysiological and/or verbal/self-report, they would be followed up with simple effect testing to identify the specific conditions and measures driving the larger multivariate effect. We would additionally test for linear and quadratic contrasts for the group comparisons in order to establish dose-dependent learning, and its gating by dopamine gene score, effects on these primary DVs. All analyses would be completed prior to breaking the blind in order to minimize bias.

*Defining dopaminergic resting-state functional connectivity (FC).* Following the prior studies cited above (Haaker, Gaburro, Sah, Gartmann, Lonsdorf, Meier, Singewald, Pape, Morellini, & Kalisch 2013a; Kelly, de, Di, Copland, Reiss, Klein, Castellanos, Milham, & McMahon 2009), we

would define three regions-of-interest (ROIs) with which to calculate resting-state FC: 1) the substantia nigra/ventral tegmental area (SN/VTA; MNI X, Y, Z coordinates = -8, -18, -20 mm), a critical region of the dopaminergic midbrain, 2) the dorsal caudate (DC; MNI X,Y,Z coordinates =  $\pm 13, 15, 19$  mm), and the ventral (limbic) striatum (VS; MNI X,Y,Z coordinates =  $\pm 16, 12, -10$  mm). Consistent with our prior RSN FC analyses (Cisler et al. 2012; Cisler et al. 2013), we would characterize FC with these seed regions using the following approach within each individual separately. First, we would extract the first principal component timecourses of 6 mm spheres centered separately on the three ROIs. Second, the seed region timecourse would be regressed onto the timecourse of every other voxel (i.e., whole-brain analyses) using an autoregressive model (AFNIs 3dREMLfit) and using an *r*-to-*z* transformation to improve normality. This would result in a separate whole-brain spatial map, indicating its degree of FC with the seed region, for each ROI and each participant.

*Defining the effect of L-DOPA and dopamine gene score on striatal and mid-brain FC.* Between-group GLMs would analyze functional connectivity (FC) using a 3 (group: placebo vs 100 mg L-DOPA vs 200 mg L-DOPA) x 2 (cue: CS+ vs CS-) x 6 (dopamine gene score: 0 [low endogenous dopamine] – 5 [high endogenous dopamine]) between-subjects ANOVA in a whole-brain, mass univariate, approach. Covariates of non-interest would be included if the “urn” balanced randomization procedure should fail to match groups on demographic and clinical severity variables. Cluster-level thresholding would be used to correct for multiple comparisons. This approach would identify clusters of voxels where FC with the SN/VTA, DC, or VS differed significantly as a function of L-DOPA, dopamine gene score, or the interaction. This analysis establishes the engagement of the intermediate mechanism in the proposed conceptual model hypothesized to mediate dopamine neurotransmission’s pro-extinction effect.

*Testing the effect of altered resting-state FC on fear extinction learning consolidation.* Following identification of regions where FC with the DC, VS, and SN/VTA differ as a function of the L-DOPA x gene score interaction, we would then test whether individual differences in FC within these clusters predict subsequent consolidation of fear extinction learning. That is, we would test whether the hypothesized intermediate mechanism (acute dopamine neurotransmission and downstream dopaminergic neural networks) is related to the ultimate mechanism of interest (fear extinction learning). Consolidation of fear extinction learning from Day 1 would again be tested using Day 2 fear expression indices in Context A and Context B (i.e., fear extinction learning recall test) using multimodal assessments (neural circuit indices, psychophysiological, and self-report). GLMs would be used in which the outcome variable is regressed simultaneously onto the FC cluster, L-DOPA group, dopamine gene score, cue, and context. This would be repeated for the separate fear expression indices, with FDR controlling for alpha inflation due to multiple comparisons. These analyses would identify the clusters of voxels whose FC with the VS, DC, and SN/VTA predict enhanced recall on Day 2.

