## **B. Specific Aims**

**Specific Aim 1: Test the degree to which endogenous and exogenous manipulations of dopamine neurotransmission affect fear extinction learning across multiple indices.** *Hypothesis:* L-DOPA dose will interact with dopaminergic gene score to predict fear extinction learning across indices.

**Specific Aim 2: Test the degree to which post-extinction functional connectivity within dopaminergic neural networks mediates the effect of dopaminergic manipulation on fear extinction learning.** *Hypothesis:* The L-DOPA x dopaminergic gene score will predict enhanced post-extinction dopaminergic functional connectivity, which in turn predicts enhanced fear extinction recall.

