The fear extinction phase would occur in Context B (with the target stimuli presented against a blue background), during which the CS+ is no longer followed by the UCS. The shapes and background would be counterbalanced as CS+, CS-, Context A, and Context B.

The recall phase occurs ~24 hours later on Day 2, during which participants are presented with the CS+ and CS- alternating between Contexts A and B in a pseudorandom manner, and no presentations of the UCS. The alternation between the contexts allows for testing resistance to context renewal of the fear memory. Every fourth trial, participants also provide self-report ratings of the anxiety elicited from the CS+ and CS- and expectation of the UCS following each CS using a Likert Scale of 0-10. In each phase, there are 12 presentations of the CS+ and CS-.

*Resting task.* The connectivity of the mesolimbic dopaminergic system will be investigated using a standard resting state task, in which participants lie passively in the scanner for 7 minutes and are simply told to let their mind wander freely.

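### Gene score planned as a six-level factor gives the key L-DOPA by gene-score interaction 10 df that often cannot all be estimated; a numeric score with its square avoids this, and the cue factor in the resting-scan model should go

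*Combined protocol and SAP*

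**What the plan says.** The Aim 1 hypothesis is that "L-DOPA dose will interact with dopaminergic gene score to predict fear extinction learning across indices". The score is the sum of five markers, each coded 0 or 1 (Section C, genetic analysis), and so runs from 0 to 5.

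The primary framework in Section G crosses three drug groups, two cues and two contexts with a six-level score: "B [extinction context]) x 6 (dopamine gene score: 0 [low endogenous dopamine". The planned MANOVAs repeat this. Group, score, cue, context "and the interactions are entered as factors explaining variance in the multivariate combination" of each outcome set. The functional connectivity (FC) model, described as a between-subjects ANOVA, uses "2 (cue: CS+ vs CS-) x 6 (dopamine gene score" together with drug group. The last analysis in Section G is a regression in which "the outcome variable is regressed simultaneously onto the FC cluster, L-DOPA group, dopamine gene score, cue, and context", with no coding given for the score. It takes forward regions whose FC is found to "differ as a function of the L-DOPA x gene score interaction".

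The linear and quadratic contrasts in the plan are over drug group, not over the score. There is no rule for sparse or empty cells. Urn randomization balances diagnoses, age and medication, not genotype.

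On power, 35 women per group (N = 105) "would provide power > .9 to detect large effects and power ~.8 to detect medium-large effects".

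**The concern.** A sum of five binary markers puts few women at 0 and at 5. Crossing six levels with three arms therefore makes empty cells at the ends likely. When a cell is empty, the 10-df interaction cannot be estimated in full. The degrees of freedom and the hypothesis tested then depend on which cells happen to fill and on how the software handles the gap, so the trial's central test is not fixed in advance. Aim 2 inherits this, because its regions are selected by the same interaction.

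The FC model has a separate fault. It includes a CS+/CS- factor, but the data come from a scan in which "participants lie passively in the scanner for 7 minutes". There is no cue to code, so that model cannot be run as written.

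**Working it through.** **Inputs from the documents.** N = 105, 35 per arm, three arms; score 0 to 5 from five 0/1 loci. **Assumed, because not given:** carrier rates (.3 to .7 at each locus, and mixed sets), correlation between loci, alpha .05, and effect sizes. Large is taken as f = .40. For medium-large I use f = .31, where a 2-df test has power of about .8, or f = .325, the midpoint of .25 and .40.

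**The plan's own power figure.** It cannot be derived, because no test, df, alpha or numeric effect size is stated. It is consistent with several tests:
- Two-group t-test, 35 per group: .91 at d = .80 and .80 at d = .68.
- 2-df F test, N = 105: .96 at f = .40 and .81 at f = .31.
- 10-df MANOVA interaction: see below.

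**Degrees of freedom.** 3 x 6 = 18 cells; (3 - 1)(6 - 1) = 10 df; 105/18 = 5.8 women per cell on average, but unevenly spread.

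**Empty cells, carrier rate .5, independent loci.** P(score 0) = P(score 5) = 1/32, so 35/32 = 1.09 women are expected in each end cell. Per arm:
- A given end cell is empty: (31/32)^35 = .329.
- Both are empty: (30/32)^35 = .104.
- Both are filled: 1 - 2(.329) + .104 = .446.
- Both are filled in all three arms: .446^3 = .089.

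So at least one end cell is empty with probability about .91. Simulation over all 18 cells also gives .91, with 2.0 empty cells and 8.1 estimable interaction df on average. Under independence, P(score 0) x P(score 5) cannot exceed (1/4)^5, so about 91% is a floor for any set of rates.

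| Assumption | P(at least one empty cell) |
|---|---|
| Independent, all .5 | 91% |
| Independent, mixed .3 to .7 | 96% |
| Independent, all .4 or all .6 | 98% |
| Independent, all .3 or all .7 | over 99.9% |
| Pairwise correlation .05, mean .5 | 70% |
| Correlation .10 | 44% |
| Correlation .20 | 12% |
| Four loci kept, all .5, independent | 49% |

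The last row matters because the plan drops any variant that fails Hardy-Weinberg equilibrium.

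**Nominal univariate power.** Noncentral F with lambda = f^2 x 105, which is 16.8 at f = .40 and 10.1 at f = .31. Error df are 87, 96 and 99.

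| Interaction test | f = .40 | f = .31 |
|---|---|---|
| Six-level factor, 10 df | .77 | .50 |
| Score and score squared, 4 df | .91 | .70 |
| Linear score only, 2 df | .96 | .81 |

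Each row assumes that the tested terms capture the whole interaction. Simulation with realised cell counts checks this. Over 27 inverted-U shapes at f = .40 (carrier rates .5 and .6), the factor test on filled cells had power .69 to .77 and the 4-df test .82 to .90. At f = .31 the ranges were .44 to .53 and .59 to .68. For an irregular pattern across cells the order reverses: about .76 for the factor against .44 for 4 df at f = .40.

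**MANOVA power, the scale Aim 1 uses.** Pillai form with p outcomes and h hypothesis df: s = min(p, h), lambda = f^2 x 105 x s, numerator df p x h. The same f implies a larger total effect here, so these values are not comparable with the univariate ones.

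| Test | Two outcomes, f = .40/.325 | Three outcomes, f = .40/.325 |
|---|---|---|
| 10 df | .95/.78 | .99/.90 |
| 4 df | .99/.93 | over .99/.98 |

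**The case against.** Four points on the other side have weight.

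First, the 3 x 6 notation may be shorthand for a score range, since the plan also speaks of GLMs and regression. That is possible, but entering the term as a factor in a MANOVA or ANOVA points the other way, and no numeric coding is stated anywhere.

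Second, the empty-cell risk rests on assumptions about carrier rates and independence that the documents do not supply. This stands. The risk falls to 12% at correlation .20. Nor does an empty cell stop the analysis: a test on the filled cells still runs, with about 8 df on average at carrier rate .5. What is lost is the full 10-df hypothesis and a test fixed in advance.

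Third, the numeric model is not uniformly better. It loses clearly for irregular patterns, and it gives up power to the 2-df test if moderation is purely linear. Its squared term also leans on the ends of the score: at carrier rate .5, about 2 of 35 women per arm have score 0 or 5, and they supply on average about 47% of the within-arm information on that term.

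Fourth, a reader might infer from the univariate .77 that the stated power is wrong. The documents do not support this. Aim 1 is tested by MANOVA, where the 10-df interaction broadly meets both stated figures. The univariate values apply to a single-outcome test, and even for the voxelwise FC model they are only nominal, because that model uses cluster thresholding.

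**Conclusion.** The concern holds for coding and estimability. As written, the Aim 1 interaction has 10 df over 18 cells. With five independent loci all kept, at least one cell is empty in about 91% of trials or more; correlation between loci or loss of a locus lowers this. The cue factor in the resting-scan model is an error whatever the genetics.

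The gain in power is conditional. For a smooth linear or inverted-U dependence, which the non-linear rationale in Sections A and C implies, nominal univariate power rises from about .77 to .91 at f = .40 and from .50 to .70 at f = .31. It would go too far to call the numeric model stronger in general.

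The power statement is unanchored, not shown to be wrong. The documents also do not say which cue or context term carries the Aim 1 test, and they give no ground for ranking the context-averaged effect above the context effect. That choice is the sponsor's. This should be fixed before unblinding, and it needs no new data.

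**What to change.** 1. Throughout the data-analysis part of Section G, define the gene score as the sum over retained loci, entered as a centred numeric variable with its square.
2. Test group x (score + score squared) jointly, 4 df, within each planned MANOVA and in the FC model. Report the 2-df group x linear-score component alongside. Use the same coding in the final regression and in the dose contrasts.
3. Remove the cue factor from the FC model.
4. Keep the cue and context terms of the Aim 1 design, and name which of them carries the Aim 1 test.
5. If power is restated, give the test, df, alpha and effect-size scale. For Aim 1 use the MANOVA scale: the 4-df test has about .99/.93 with two outcomes and over .99/.98 with three, at f = .40/.325. Give any univariate test separately; .91/.70 alone would not describe Aim 1.
6. If the six-level factor is kept, state its power on the scale used and a rule for empty cells.

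Cost: wording only, with no extra participants or measurements. The price is the assumption of an at most quadratic dependence on the score within each arm, some power lost to the 2-df test if moderation is linear (.91 against .96 at f = .40), and reliance on the few women at the ends of the score.

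### Day 1 pre-pill responding, age and comorbid diagnoses are adjusted for only if arms differ, which gives up precision that the collected data could supply

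*Combined protocol and SAP*

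**What the plan says.** Section G, Primary Analytic Framework, describes a "mixed design focused on Day 2 fear responding". Preliminary analyses look for baseline "differences in fear responding or extinction learning on Day 1 and include these variables as covariates if needed".

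Planned Fear Extinction Analyses repeats the rule for the MANOVAs: "any factors that differ between groups, such as Day 1 fear responding, age, or comorbid diagnoses, would also be entered as covariates", should the urn randomisation fail. The paragraph on L-DOPA and gene score effects on FC adds covariates if the "balanced randomization procedure should fail to match groups on demographic and clinical severity variables".

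No threshold is given for what counts as differing, being needed, or failing. No other section makes Day 1 responding, age or comorbid diagnoses a fixed covariate. Medication is different: Study Population says without condition that it will be modelled. The ancestry wording in section G can be read as unconditional. This point concerns neither.

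Two design facts matter. First, Study Design places the pill after the roughly 40-minute Day 1 scan. Acquisition and extinction, each with 12 presentations of CS+ and CS-, therefore precede treatment, and heart rate and skin response are recorded during scanning. Second, Balanced Randomization names comorbid diagnoses, age and medication as the urn factors.

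**The concern.** After randomisation, arm differences at baseline are chance events. Testing for them says nothing about whether a variable predicts Day 2 responding, which is what decides whether adjustment reduces error variance. A balance-test trigger therefore usually drops a predictive baseline. For the urn factors, the procedure that balances them also makes it less likely that they are modelled.

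What is at stake is the power of the randomised drug and drug x gene score tests on Day 2 CS+ minus CS-, in a trial of 35 per arm. The undefined trigger also leaves the final model open until data are seen.

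**Working it through.** **Inputs from the plan.** 35 per arm and N = 105; power above .9 for large and about .8 for medium-large effects (section G, Power Analyses). Gene score 0-5 as a six-level factor (Primary Analytic Framework).

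**Assumptions, because the documents do not state them.** Alpha .05 before FDR; Day 1-Day 2 correlation r from .2 to .5; a 5% F-test as the trigger; the gene score distribution.

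**The plan's own figure.** The plan gives no numerical effect size and names no test, so its power cannot be strictly reproduced. For a three-group comparison (2 and 102 df), f = .40 gives .96, f = .25 gives .61, and .80 needs f = .307. The stated values are plausible. I use f = .31 because it gives about .8 for the 2-df interaction test; the plan does not tie its .8 to that test.

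**How often the baseline is left out.** For one index, 1 - .05 = .95. With three Day 1 terms, at least one is flagged with probability 1 - .95^3 = .14, which agrees with simulation (14%).

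**Single index.** Noncentrality is f^2 x N/(1 - r^2), and unadjusted .31^2 x 105 = 10.09. With a linear score the error df are 105 - 6 = 99, and with the six-level score 105 - 18 = 87. The Day 1 term takes one.

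| r | 10.09/(1 - r^2) | Power, 2 df | Power, 10 df |
|---|---|---|---|
| unadjusted | 10.09 | .807 | .496 |
| .2 | 10.51 | .823 | .516 |
| .3 | 11.09 | .844 | .543 |
| .4 | 12.01 | .873 | .585 |
| .5 | 13.45 | .909 | .646 |

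In precision, r = .3 corresponds to an unadjusted N of 105/.91 = 115, and r = .5 to 105/.75 = 140.

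In simulations of the 2-df test (5,000-6,000 replicates, linear score Binomial(5, .5)), the conditional rule stays at .80-.82 at every r. A looser p < .20 trigger reaches only .82-.83 at r = .5. Adding three urn factors that predict nothing gives .81, .83, .86 and .90 at r = .2, .3, .4 and .5. If they explain 5% of the variance, it gives .84, .85, .89 and .91.

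**Three-variable MANOVA.** Wilks test, equicorrelation .3, effect set for about .81 unadjusted, every Day 1 term entering for every dependent variable:
- Conditional rule: .80-.82.
- Day 1 always: .81-.82, .83-.84, .87 and .91 at r = .2, .3, .4 and .5.
- Day 1 plus three non-prognostic urn factors: .80, .82, .86 and .90.
- Only one index correlated, r = .3: .803 against .803, no gain.
- Only one index correlated, r = .5: .845 against .812.

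**Six-variable MANOVA.** The ROI paragraph sends six indices into the MANOVA, whereas the MANOVA paragraph lists three regions. With six, the Day 1 terms lose about .02 at r = .2, gain about .01 at r = .3, and help clearly only from about r = .4. With three non-prognostic urn factors added, adjusted against unadjusted power is .80 against .82 (r = .2), .83 against .83 (r = .3) and .90 against .81 (r = .5).

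**Type I error of the conditional rule.** It is .051 in the three-variable MANOVA. In a plain three-group comparison it is .048, .046 and .038 at r = .3, .5 and .7.

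**The case against.** The strongest reply is that the plan specifies MANOVAs ("We would conduct three sets of MANOVA analyses, one with the set of Day 2 neural circuit indices"), and there the gain depends on an r that nobody has stated. With urn factors that predict nothing, the three-variable MANOVA shows no net gain up to about r = .3, and the six-variable version loses power at r = .2. Day 1 is also an imperfect baseline: acquisition is run in one context, extinction in the other, and Day 2 alternates both. The CS+ minus CS- contrast may already remove some stable between-person variance, so r may be low. All of this stands. It limits the size of the benefit and favours fits in which each outcome carries only its own Day 1 term. It does not defend a balance test as the trigger.

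It is also fair that 95% rests on a 5% test, since the plan's trigger could be a matter of judgement. The 10-df figures rest on an even spread of gene scores. Under a Binomial(5, .5) score an arm lacks score 0 with probability (31/32)^35 = .33, and likewise score 5. At least one of those six cells is then empty in about 1 - .67^6 = .91 of trials, so the six-level test would often not be estimable as written.

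A reader might infer three stronger claims that the documents do not support:
- **Bias or false positives.** The computed error rates do not exceed .05 beyond simulation error, and the plan says "All analyses would be completed prior to breaking the blind in order to minimize bias".
- **The same precision gain in the models relating FC to recall.** There "GLMs would be used in which the outcome variable is regressed simultaneously onto the FC cluster, L-DOPA group, dopamine gene score, cue, and context". FC is measured after the pill and is not randomised, so a Day 1 term would serve confounding control, a different argument that is not made here.
- **Site can be ignored for CS+ minus CS-.** Only an additive site offset cancels; the documents do not rule out a difference in signal scale.

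**Conclusion.** The point holds as a loss of efficiency and an underspecified model, not as an invalid test. Conditional adjustment recovers almost none of the available gain. For a single index with about .8 unadjusted power, always adjusting is worth about .02 at r = .2, .04 at r = .3, .07 at r = .4 and .10 at r = .5. The three-variable MANOVA is similar from r = .3 upward but gains almost nothing at r = .2. The six-variable MANOVA benefits clearly only from about r = .4.

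These figures assume 35 analysed per arm, alpha .05 before FDR, and an effect chosen to give about .8. No gain is claimed for context interactions, because no Day 1 phase crosses cue with context. The benefit in the FC models has not been quantified. The change is worth making but not critical; confidence is moderate because r is unknown.

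**What to change.** In Primary Analytic Framework and Planned Fear Extinction Analyses, replace the balance-test trigger with adjustment prespecified regardless of observed balance.

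1. **Day 2 models.** Enter the Day 1 pre-pill CS+ minus CS- response for the same index as covariate x cue, from one named phase. Extinction is cleaner, because the UCS overlaps about half of the 12 acquisition CS+ trials; if acquisition is used, restrict it to unreinforced CS+ trials. Fit per index or in a mixed model, so that each outcome carries only its own Day 1 term. Apply this only to indices with a Day 1 cue-level value. Confirm self-report first, because the ratings are described only in the recall paragraph.
2. **Day 2 and FC models.** Enter age, comorbid diagnoses and medication, coded compactly. FC gets no Day 1 term, because no pre-pill resting scan is described. A site term in the FC models is optional.

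The cost is SAP wording and a few error df: one for Day 1 per index and about three for the urn factors, out of at most 87 with the six-level score. If the urn factors are not prognostic they cost about .01-.02 power, and at low r there is no net gain. Per-index testing would enlarge the set of tests under FDR, so the SAP should name that set.

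### The neural outcomes are already CS+ versus CS- contrasts, yet cue is still entered as a factor, so the cue terms are inestimable there and L-DOPA x gene score tests something different from the same term for self-report

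*Combined protocol and SAP*

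**What the plan says.** Section G, Data analysis, sets the Aim 1 framework as group by cue (two levels) by context (two levels) by gene score. The paragraph on neural circuit ROI definition and extraction describes the first-level result as a map, "resulting in a whole-brain spatial map indicating the degree to which each voxel responds to CS+ vs CS- during Context A vs B", and then defines what is taken from it: "The mean contrast values for CS+ vs CS- as a function of context is then extracted from the voxels". It counts the output as follows: "These analyses would provide six (for each ROI) indices of activation, calculated separately for each participant".

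The paragraph on planned fear extinction analyses lists three MANOVAs (neural, physiological, verbal/self-report) and says of all three that "the mixed effects of L-DOPA group, dopamine gene score, cue, context, and the interactions are entered as factors explaining variance". FDR correction is applied because there are three sets of tests; the effect that each set contributes is not named.

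For Aim 2, the paragraph on altered resting-state FC and consolidation names neural, psychophysiological and self-report outcomes, and specifies GLMs in which the "outcome variable is regressed simultaneously onto the FC cluster, L-DOPA group, dopamine gene score, cue, and context". These terms are additive.

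Section C, MRI Procedures, says that anxiety and UCS expectation are rated separately for CS+ and CS-. No passage says how SCR, HR or HRV are scored by cue. No passage says that separate CS+ and CS- neural estimates are kept, or that cue is dropped from the neural models.

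**The concern.** A variable formed by subtracting CS- from CS+ has one value per context, and cue has a single level in it. Cue and its interactions therefore have nothing to act on in the neural models.

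The larger issue is what the surviving terms mean. Specific Aim 1 hypothesises an L-DOPA by gene score interaction across indices. On a neural contrast, that interaction is an effect on conditioned fear. On ratings held per cue, the term of the same name is an effect on responding averaged over CS+ and CS-, and conditioned fear is the three-way interaction with cue. The Aim 2 GLM has the same split: the FC coefficient predicts the cue difference for neural outcomes and the cue average for self-report, because the model has no FC x cue term. A reader who compares the same-named effect across sets, or pools its p-values in the FDR step, would be combining different questions.

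**Working it through.** **Plan's own figure.** The only nearby figure is power with 35 per group (N = 105). With alpha 0.05 (assumed; the plan gives none) and a three-group one-way F test, effect size f = 0.40 gives power 0.960, consistent with the stated > .9. Power of 0.80 needs f = 0.307. This point neither disputes nor changes those figures.

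**Count of effects.** Four factors give 2^4 - 1 = 15 main effects and interactions. Those containing cue number 2^3 = 8, which leaves 7.

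**Rank of the Aim 1 design.** Take gene score as linear (an assumption). The between-subject part has 6 columns: intercept, two for group, one for gene score, two for group x gene score. The within-subject part has 4: constant, cue, context, cue x context.
- One estimate per cue and context: 105 x 4 = 420 rows and 6 x 4 = 24 columns; rank 24, so all terms are estimable.
- CS+ minus CS- per context: 105 x 2 = 210 rows; rank 6 x 2 = 12 of 24. No cue term is identified.
- If the first-level map is instead differenced over context too: 105 rows, rank 6 of 24, and context is lost as well.

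**Rank of the Aim 2 GLM.** Columns: intercept, FC, two for group, gene score, cue, context = 7. With one estimate per cue and context the rank is 7. With a contrast outcome it is 6, because cue duplicates the intercept. FC, group, gene score and context remain estimable.

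**What L-DOPA x gene score measures.** Noise-free slopes for one dose group against placebo:

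| Slope on CS+ / CS- | Average over cues | CS+ minus CS- |
|---|---|---|
| 0.5 / 0.5 | 0.50 | 0.00 |
| 0.5 / 0 | 0.25 | 0.50 |
| 0.5 / -0.5 | 0.00 | 1.00 |

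The second and third columns are the same-named term in a model held by cue and in a model on the contrast.

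**Illustrative power.** Assume an effect d on CS+ only, equal SD s for the two cues, correlation rho between them, a 1-df test and alpha 0.05. The documents give no rho.
- Cue difference: standardised effect d / (s x sqrt(2(1 - rho))).
- Cue average: (d/2) / (s x sqrt((1 + rho)/2)).
- Squared ratio, average to difference: (1 - rho)/(1 + rho).

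If the difference test has 80% power, its expected z is 1.96 + 0.84 = 2.80, and the average test has power of about Phi(2.80 x sqrt(ratio) - 1.96):

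| rho | Ratio | Power, cue average |
|---|---|---|
| 0 | 1.00 | 80% |
| 0.2 | 0.67 | 63% |
| 0.5 | 0.33 | 37% |
| 0.8 | 0.11 | 15% |

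**The case against.** The strongest reply is that contrast values may be loose wording for condition estimates. The framework sentence has cue as a two-level factor, and the first-level GLM models both cues in both contexts, so separate estimates can be obtained. That is possible, but the plan does not say so, and the extraction sentence says the opposite.

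A second reply is that nothing is lost, since software drops cue and the rest is fitted. This stands in part. A reader might infer that the neural MANOVA or the Aim 2 GLM cannot be run at all. That does not follow: 7 of the 15 Aim 1 effects remain, L-DOPA x gene score on the contrast is itself the neural conditioned-fear test, and its interaction with context is the renewal test. In the Aim 2 GLM only the single additive cue term is affected, and only for neural outcomes; that model has no cue interactions to lose. What does not go away is the change of meaning between sets.

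A reader might also want six indices corrected to twelve. The documents do not support that: six counts dependent variables, one per ROI, with context as a repeated factor.

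Third, the loss of power is conditional. The MANOVAs for outcomes held by cue already include L-DOPA x gene score x cue, and the plan does not say which effect enters the FDR step. The loss arises only if the two-way term is carried forward. This stands, and it is why the figures are offered as a range only.

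**Conclusion.** The definition of the neural outcome and the factor lists contradict each other and must be reconciled. If the outcome is a contrast by context, 8 of 15 Aim 1 effects are inestimable for the neural set and cue is aliased in the Aim 2 GLM for neural outcomes; both models can be fitted without those terms.

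The mismatch in estimand is established between the neural set and self-report, because ratings are documented per cue. It extends to SCR, HR and HRV only if they are scored per cue, which the documents leave undefined. It would be inferring too much to treat it as shown for all three sets, or to treat a power loss as demonstrated: the range from 80% down to 15% rests on an effect confined to CS+, a 1-df test, alpha 0.05 and an assumed correlation between 0 and 0.8. The actual tests have more degrees of freedom and are multivariate.

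This is more than a missing detail. Aim 1 states its hypothesis as L-DOPA by gene score across indices, and the Aim 2 GLM has no FC x cue term, so following the text tests conditioned fear in one set and cue-averaged responding in another.

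**What to change.** Choose one of the following before analysis.

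(a) Extract one estimate per cue and context for each ROI, so that cue is a real factor in the neural models. Name L-DOPA x gene score x cue, and its interaction with context, as the Aim 1 test matched across sets. Add FC x cue to the Aim 2 GLM as its test of interest.

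(b) Keep the CS+ minus CS- contrast and delete cue from the neural models for both aims. Use the same difference, for both aims, for every other outcome that is scored per cue, and drop cue there too. Name L-DOPA x gene score on that difference, and its interaction with context, as the matched Aim 1 test, and FC on that difference as the Aim 2 test.

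Under either choice, state which effect from each set enters the FDR step, and state whether SCR, HR and HRV are scored per cue. Any that are not cannot enter the matched conditioned-fear test and should be reported separately.

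The cost is wording in the statistical plan, with no new data and no change in sample size. Option (b) has one small downside: responding common to both cues becomes a descriptive report.
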